6.15.7. Columbia-Suicide Severity Rating Scale (C-SSRS)

The Columbia-Suicide Severity Rating Scale (C-SSRS) is an assessment tool that evaluates suicidal ideation and behavior. Information on the C-SSRS scale can be found through the following link: <http://www.cssrs.columbia.edu>.

Specifically, the following outcomes are C-SSRS categories and have binary responses (yes/no). The categories have been re-ordered from the actual scale to facilitate the definitions of the composite and comparative endpoints, and to enable clarity in the presentation of the results.

Category 1 – Wish to be Dead

Category 2 – Non-specific Active Suicidal Thoughts

Category 3 – Active Suicidal Ideation with Any Methods (Not Plan) without Intent to Act

Category 4 – Active Suicidal Ideation with Some Intent to Act, without Specific Plan

Category 5 – Active Suicidal Ideation with Specific Plan and Intent

Category 6 – Preparatory Acts or Behavior

Category 7 – Aborted Attempt

Category 8 – Interrupted Attempt

Category 9 – Actual Attempt (non-fatal)

Category 10 – Completed Suicide

Self-injurious behavior without suicidal intent is also a C-SSRS outcome (although not suicide-related) and has a binary response (yes/no).

Composite endpoints based on the above categories are defined below.

- Suicidal ideation: A “yes” answer at any time during treatment to any one of the five suicidal ideation questions (Categories 1-5) on the C-SSRS.
- Suicidal behavior: A “yes” answer at any time during treatment to any one of the five suicidal behavior questions (Categories 6-10) on the C-SSRS.
- Suicidal ideation or behavior: A “yes” answer at any time during treatment to any one of the ten suicidal ideation and behavior questions (Categories 1-10) on the C-SSRS.

Given that few or no suicidal ideation or behaviors are anticipated, C-SSRS will be listed by patient and visit. Only patients that show suicidal ideation/behavior or self-injurious behavior without suicidal intent will be displayed (i.e., if a patient answers are all ‘no’ for the C-SSRS, then that patient will not be displayed). However, if a patient reported any suicidal ideation/behavior or self-injurious behavior without suicidal intent at any time point then all their ideation and behavior will be displayed, even if not positive.

Note that missing data should not be imputed.

6.16. Immunogenicity

6.16.1. Definitions and Terms

The following sample- and patient-related definitions and parameters will be used to describe the immunogenicity data.

6.16.1.1. Sample Category Definitions

Samples are classified into the following categories:

- **Unevaluable sample:** Sample could not be tested for ADA due to sample loss, mishandling, or errors in collection, processing, storage, etc.
- **Anti-drug antibody (ADA) Positive sample:** The presences of ADA is detected and confirmed. The samples are reported as positive. If the sample is positive, a titer value is reported.

- **Neutralizing anti-drug antibody (NAb) Positive sample:** NAb are reported as detected.
- **Antidrug antibody (ADA) Negative sample:** The presence of ADA is not detected and the assay drug tolerance level is not exceeded.
- **NAb Negative sample:** The presence of NAb is not detected and the assay drug tolerance level is not exceeded.
- **Inconclusive sample:** when ADA/NAb is not detected in a sample but drug is present in the same sample at a level that can cause interference in the ADA/NAb detection method, then the negative ADA/NAb result cannot be confirmed and the sample should be considered inconclusive.
 - Confirmation of a negative ADA result is based on observed/measured ixekizumab levels. Ixekizumab concentration allows for confirmation of negative NAb results.

Figure RHBQ.6.1 illustrates the relationship of some of the above terms.

[figure not shown]

Figure RHBQ.6.1. Sample definitions.

6.16.1.2. Patient Category Definitions

The following categories are applied to patients based on the classification of their samples:

- **Unevaluable patient:**

- a) a patient with no evaluable baseline sample and/or no evaluable post-baseline samples or
 - b) a patient with an evaluable baseline sample but no evaluable post-baseline sample or
 - c) a patient with no evaluable baseline sample, but whose evaluable post-baseline values are all ADA positive or a mix of positive and negative. (Note: If all post-baseline samples are negative, the patient is considered ‘evaluable’ and will be classified as ADA-negative.)
- **Evaluable patient:**
 - a) a patient with an evaluable baseline sample and at least 1 evaluable post-baseline sample (that is, sample after administration of study drug) or
 - b) a patient with no evaluable baseline sample whose evaluable post-baseline samples are all ADA negative.

Figure RHBQ.6.2 illustrates the relationship of the above terms.

[figure not shown]

Figure RHBQ.6.2. Patient categories (evaluable/unevaluable) based on sample status at baseline and post-baseline.

6.16.1.3. Definitions for Clinical Interpretation of Assay Results

- **Baseline:** For immunogenicity analyses during Period 2, baseline is the last non-missing observation on, or prior to, the date of the first injection of study treatment of ixekizumab

(Week 0). Unless otherwise specified, the baseline for subsequent treatment periods is defined as the last non-missing observation on, or prior to, the date of first injection of ixekizumab. For patients originally randomized to ixekizumab during Period 2, baseline is the last non-missing observation on, or prior to, the date of the first injection of study treatment for Period 2 (Week 0). For patients who are not originally randomized to ixekizumab in Period 2, baseline is the last non-missing observation on, or prior to, the date of the first injection of ixekizumab. See [Table RHBQ.6.8](#) for further details.

Table RHBQ.6.8. Baseline Definition for Immunogenicity Analyses for Extended Treatment Period

Treatment Assignment for Blinded Treatment Period (Period 2)	Treatment Assignment for Open-Label Treatment Period (Period 3)	Baseline for Open-Label Treatment Period Analysis ^a
Ixekizumab	Ixekizumab	Week 0
Placebo	Ixekizumab	Week 12

^a Last non-missing observation on, or prior to, the date of the first injection of study treatment at the defined week.

- **Baseline ADA positive (pre-existing antibody):** ADA detected in a sample collected at baseline.
- **TE-ADA positive:** a) a patient with a ≥ 4 -fold increase over a positive baseline antibody titer (Tier 3); or b) for a negative baseline titer, a patient with an increase from the baseline to a level of $\geq 1:10$.
- **Baseline ADA-negative:** ADA is not detected in a sample collected at baseline.
- **TE-ADA inconclusive patient:** A patient without a TE-ADA positive sample and with at least one sample for which drug levels may interfere with the ADA assay.
- **TE-ADA negative patient:** A patient who is evaluable for TE-ADA and is not either TE-ADA positive or TE-ADA inconclusive.

[Figure RHBQ.6.3](#) illustrates the relationship of some of these terms.

[figure not shown]

Figure RHBQ.6.3. Relationship of terms for clinical interpretation of assay results for evaluable patients.

- **Incidence of TE-ADA:** Patients with TE-ADA as a proportion of the evaluable patient population during the treatment period. This excludes unevaluable patients.
- **Follow-up emergent ADA:** ADA is first detected during the follow-up period, after study drug administration is discontinued. This category includes patients negative at baseline who increased to $\geq 1:10$ titer (4-fold increase/2 dilutions) after baseline in the follow-up period or patients ADA positive at baseline and increased at least 4-fold (2 dilutions) over baseline for the first time in the follow-up period.
- **Incidence of follow-up emergent ADA:** Patients with follow-up emergent ADA as a proportion of the follow-up evaluable patient population. This excludes unevaluable patients.

All ADA positive samples will be evaluated for NAb. Definitions for NAb patient status will be defined as follows:

- **NAb-positive patient:** A patient where a NAb positive result is detected for ≥ 1 TE-ADA positive samples.
- **NAb-inconclusive patient:** A patient without a NAb positive sample and with at least one sample for which drug levels may interfere with the NAb assay.
- **NAb-negative patient:** A patient who is evaluable for NAb and is not either NAb positive or NAb inconclusive.

A flow chart that reflects the connection between the analytical test results and the clinical interpretation based on the definitions is shown in [Figure RHBQ.6.4](#).

[figure not shown]

Figure RHBQ.6.4. Flow chart of ADA assessment with clinical interpretation of the various result possibilities.

For each TE-ADA status dichotomous variable, a time-varying TE-ADA status will be computed. At time *t* the TE-ADA status is taken to be the highest of the TE-ADA values bracketing time *t*. More formally, the TE-ADA status at time *t* is given by the greater of (a) the TE-ADA status at the most-recent post-baseline measurement prior to *t*, and (b) the TE-ADA status at the first TE-ADA post-baseline measurement at or after time *t*. In this computation, 'greater' is given by the greater-TE-ADA status of [Table RHBQ.6.9](#). If there is no value

satisfying criterion (a), then the value (b) is used. Similarly, if there is no value (b), then the value (a) is used.

For each TE-ADA status dichotomous variable, patients will be categorized according to whether they were (i) always in lesser-TE-ADA status post-baseline or (ii) at some point post-baseline, were in greater-TE-ADA status.

6.16.2.1. Analyses of Characteristics of ADA Immune Response

The analyses of ADA effects will be conducted on all evaluable patients within the defined safety population for the Blinded Treatment Period (Period 2), Open-label Treatment Period (Period 3) and within the defined follow-up population for the Post-Treatment Follow-up Period (Period 4).

The overall frequency and percentage (incidence) of patients will be summarized for the TE-ADA status groups and the time-varying TE-ADA status groups. Scheduled visits, unscheduled visits, and repeat measurements will be included.

The time to the development of TE-ADAs (TE-ADA positive, low titer, moderate titer, high titer, and NAb positive) will be calculated as follows:

$$\text{Time to development of TE-ADAs/NAb (in weeks)} = (\text{Date of development of TE-ADAs/NAb} - \text{Date of first injection of study treatment} + 1) / 7.$$

If a patient has not developed TE-ADAs/NAbs, they will be censored at the date of the last immunogenicity assessment. If a patient does not have any post-baseline assessments for immunogenicity, they will be censored at the date of randomization.

Descriptive statistics, including 25th percentile, 50th percentile (median), 75th percentile, and corresponding 95% confidence intervals as well as probability of TE-ADA/NAb positive by endpoint summarized by treatment group, will also be provided if sufficient data is present. A Kaplan-Meier plot of the time to development of treatment-emergent ADA/NAb will be presented by treatment group, also if sufficient data is present. The log-rank test will be used to test the null hypothesis against the alternate hypothesis that the time to TE-ADA/NAb is not equal between each ixekizumab dose and placebo. Caution should be exercised in the interpretation of time-to event analyses, and related statistics, given the limited sampling scheme for immunogenicity testing.

For each TE-ADA status dichotomous variable (as defined in Table RHBQ.6.9), summaries will be provided of the total post-baseline time in the greater-TE-ADA status for patients who were at some point post-baseline in the greater-TE-ADA status group. Post-baseline time in greater-TE-ADA status for each patient will be aggregated.

A by-patient listing to include treatment, visit date, visit, ADA result, TE-ADA result, NAb result, ADA titer value, ixekizumab concentration, ADA and NAb inconclusive results will also be provided for the individual studies, for patients with any one sample of ADA (or NAb) positive or inconclusive.

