5.1. Overview of Study Design

Study I1F-MC-RHBQ (RHBQ) is a Phase 3, multicenter, randomized, double-blind, placebo-controlled, parallel-group, outpatient study examining the efficacy and safety of ixekizumab as compared to placebo in patients with moderate-to-severe genital psoriasis. The study consists of 4 periods:

- **Period 1: Screening Period** (Visit 1 and Visit 1A) will assess patient eligibility and start e-diary data collection, occurring approximately 7 to 30 days prior to Period 2 (baseline; Week 0; Visit 2).
- **Period 2: Blinded Treatment Period** will occur from Week 0 (Visit 2) up to Week 12 (Visit 7). Patients will be randomized to ixekizumab or placebo in a 1:1 ratio. Two injections of ixekizumab 80 mg subcutaneous (SC) (total dose of 160 mg) or 2 injections of placebo SC, respectively, will be given at Week 0 (Visit 2). From Week 2 through Week 10 patients will receive ixekizumab 80 mg every 2 weeks (Q2W) SC or placebo Q2W SC.
- **Period 3: Open-Label Treatment Period** will occur from Week 12 (Visit 7) up to Week 52 (Visit 12). At Week 12 (Visit 7) 1 injection of ixekizumab 80 mg SC and 1 injection of placebo SC (total dose of ixekizumab 80 mg) will be given to patients who were randomized to ixekizumab in Period 2; and 2 injections of ixekizumab 80 mg SC (total dose of ixekizumab 160 mg) will be given to patients who were randomized to placebo in Period 2. During the remainder of Period 3, patients will receive ixekizumab 80 mg every 4 weeks (Q4W) dosing with an option to step-up to Q2W dosing starting at Week 24 through Week 40 (at Visit 9 [Week 24], Visit 10 [Week 28], or Visit 11 [Week 40]). This Open-label Treatment Period will allow evaluation of long-term efficacy and safety of ixekizumab through 1 year (52 weeks).
- **Period 4: Post-Treatment Follow-up** (Visit 801 through Visit 803) is for safety monitoring after treatment discontinuation for any patient receiving at least 1 dose of investigational product. Once patients complete the study treatment or discontinue study treatment early, patients will complete the Post-Treatment Follow-up (Period 4). For patients who have entered Period 4, psoriasis therapy is allowed, as determined appropriate by the investigator. This period occurs from the last treatment period visit or early termination visit (ETV) up to a minimum of 12 weeks following that visit.

Figure RHBQ.5.1 illustrates the study design.

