6.1.1. Analysis Populations

Intent-to-treat Population: The Intent-to-treat (ITT) Population consists of all randomized patients. Even if the patients are not administered the assigned treatment, do not receive the correct treatment, or otherwise do not follow the protocol, they will be analyzed according to the treatment group to which they were assigned. Unless otherwise specified, all efficacy and health outcomes analyses during the Blinded Treatment Period will be conducted on the ITT Population.

Safety Population: The Safety Population is defined as all randomized patients who received at least 1 dose of study treatment. Patients will be analyzed according to the treatment group to which they were assigned. Unless otherwise specified, all safety analyses during the Blinded Treatment Period will be conducted on the Safety Population.

Open-label Treatment Population: The Open-label Treatment Population consists of all randomized patients who received at least 1 dose of study treatment during Period 3 and have entered the Open-label Treatment Period. Patients will be analyzed according to the treatment group to which they were assigned in Period 2, unless otherwise specified. All analyses for Period 3 (Open-label Treatment Period) will be conducted on this analysis population.

Post-Treatment Follow-Up Population: The Post-Treatment Follow-up Population consists of all randomized patients who received at least 1 dose of study treatment during Period 2 and have entered the Post-Treatment Follow-up Period. Patient data will be summarized according to the treatment group that the patient is assigned prior to entering the Post-Treatment Follow-up Period. Safety analyses for Period 4 (Post-Treatment Follow-up Period) will be conducted on this analysis population.

Table RHBQ.6.1. Treatment Group and Comparisons for Each Study Period and Analysis Population

Study Period	Analysis Population	Treatment Group	Abbreviation	Comparison
Blinded Treatment Period (Period 2)	Intent-to-treat Population; Safety Population	Ixekizumab 80 mg Q2W	IXE80Q2W	IXE80Q2W vs. PBO
		Placebo	PBO	
Open-label Treatment Period (Period 3)	Open-label Treatment Population	Ixekizumab 80 mg Q2W / Ixekizumab 80 mg Q4W	IXE80Q2W/IXE80Q4W	No comparison
		Placebo / Ixekizumab 80 mg Q4W	PBO/IXE80Q4W	
Post-Treatment Follow-up Period (Period 4) ^a	Post-Treatment Follow-up Population	Placebo	PBO	No comparison
		Ixekizumab 80 mg Q2W	IXE80Q2W	
		Ixekizumab 80 mg Q4W	IXE80Q4W	

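### SAP 6.16.2.1 has one clock origin for time to TE-ADA/NAb; read literally, it overstates any Period 3 time in the PBO/IXE80Q4W group by about 12 weeks

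*SAP*

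**What the plan says.** SAP 6.16.2.1 opens with the scope of the ADA analyses: evaluable patients within the "safety population for the Blinded Treatment Period (Period 2), Open-label Treatment Period (Period 3"), and the follow-up population for Period 4. It then gives a single formula for time to TE-ADA/NAb in weeks: event date minus origin date, plus 1, divided by 7. The origin is the "Date of first injection of study treatment". No period and no drug is attached to that phrase.

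Elsewhere in the SAP, study treatment includes placebo. Section 6.1.1 states: "The Safety Population is defined as all randomized patients who received at least 1 dose of study treatment", and the placebo arm belongs to that population. Section 5.1 gives the dates: "2 injections of placebo SC, respectively, will be given at Week 0 (Visit 2"), and at Week 12 two ixekizumab injections "will be given to patients who were randomized to placebo in Period 2".

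The immunogenicity baseline is defined differently. Section 6.16.1.3 says "For patients who are not originally randomized to ixekizumab in Period 2, baseline is the last non-missing observation" on or before the first ixekizumab injection, and Table RHBQ.6.8 gives Week 12 for the placebo-then-ixekizumab sequence. The table's footnote ties the baseline to "the date of the first injection of study treatment at the defined week".

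Two censoring rules go with the formula. Patients without an event are censored at their last immunogenicity assessment. The fallback is: "If a patient does not have any post-baseline assessments for immunogenicity, they will be censored at the date of randomization".

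**The concern.** For an originally-placebo patient in Period 3, the event and the clock start at different times. TE-ADA is judged against a Week 12 baseline, so no event can be counted before Week 12. The clock, read literally, has already run for 12 weeks on placebo. Those weeks are not time at risk.

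If Period 3 quartiles, medians or Kaplan-Meier curves are produced by treatment group, those for PBO/IXE80Q4W would be shifted to the right by the length of the placebo phase. A reader would take antibody formation after first ixekizumab exposure to be slower than it was. What is at stake is the accuracy of a descriptive immunogenicity summary.

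**Working it through.** The plan states no numeric result for time to TE-ADA/NAb, so there is no figure to reproduce. The check applies the SAP formula to the scheduled visits under each origin.

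**Inputs**
- Formula: (event date − origin date + 1) / 7 (SAP 6.16.2.1).
- First study-treatment injection in the placebo arm: Week 0, taken as day 0 (SAP 5.1).
- First ixekizumab injection in the placebo arm: Week 12, day 84 with a window of ±4 days (SAP 5.1; protocol Appendix 2).
- Scheduled Period 3 immunogenicity samples: Week 24 (day 168) and Week 52 (day 364), plus any early termination visit (protocol Appendix 2).
- Patients: 1:1 randomization, 73 of 146 to placebo (SAP 5.3).

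**Originally-placebo patients, nominal visit days**

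| First TE-ADA positive sample | Origin Week 0 (as written) | Origin Week 12 (first ixekizumab) | Difference |
|---|---|---|---|
| Week 24 | (168 − 0 + 1)/7 = 24.1 | (168 − 84 + 1)/7 = 12.1 | 12.0 weeks |
| Week 52 | (364 − 0 + 1)/7 = 52.1 | (364 − 84 + 1)/7 = 40.1 | 12.0 weeks |

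The recorded time is 169/85 = 1.99 times the time since first ixekizumab at Week 24, and 365/281 = 1.30 times at Week 52.

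**Range.** The shift equals the gap between the two first injections. With the Week 12 window it runs from 80/7 = 11.4 to 88/7 = 12.6 weeks. If Week 0 is numbered study day 1, as in the schedule of activities, it is 83/7 = 11.9 weeks (79/7 = 11.3 to 87/7 = 12.4). The conclusion is the same.

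**Censored times.** Censoring at the last assessment uses the same origin, so event-free patients shift by the same amount and the whole curve moves.

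**Other patients and periods.** In patients randomized to ixekizumab, the first study-treatment injection is the first ixekizumab injection, so nothing changes. In Period 2 both arms start at Week 0, which is the right origin for comparing them.

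**Fallback censoring date.** As written, censoring at randomization gives (0 − 0 + 1)/7 = 0.1 week. That is before any post-baseline sample, so the patient is in no risk set when an event is recorded and cannot move the curve. SAP 6.16.1.2 also classes a patient with no evaluable post-baseline sample as unevaluable, so the rule reaches essentially nobody in the stated analysis population. It fails only if the origin moves and it does not: (0 − 84 + 1)/7 = −11.9 weeks.

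**The case against.** The strongest reply is that the phrase is ambiguous and not plainly wrong. The Table RHBQ.6.8 footnote uses nearly the same words for Week 12 in originally-placebo patients, and a programmer could carry that reading into the formula. This stands in part. The footnote governs the baseline only, and nothing in 6.16.2.1 imports it. Where the SAP means ixekizumab it generally says so: 6.16.1.3 refers to the first ixekizumab injection, and 6.15.1 counts combined-period exposure from the first ixekizumab dose. At the least, the Period 3 origin is left open.

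Several limits on the stakes stand in full:
- The only time-to-antibody test named is ixekizumab against placebo, which exists only in Period 2. No Period 3 Kaplan-Meier output is listed separately; Period 3 comes in through the section's scope sentence.
- The summaries depend on there being enough data, and the SAP already urges caution because sampling is sparse. That caution concerns imprecision and does not cover a constant offset.
- The immunogenicity endpoint is sPGA of Genitalia (0,1) at Week 12 by TE-ADA and NAb status, which uses no time-to-antibody variable. A by-patient listing with visit dates would let a reader recount any positive case.

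A reader might go further and infer that the offset creates a false difference between the two Period 3 groups which a new origin would remove. The documents do not support that. Table RHBQ.6.1 plans no Period 3 comparison. Scheduled samples after first ixekizumab fall at Weeks 2, 4, 12, 24 and 52 in the ixekizumab arm, but only about 12 and 40 weeks after first exposure in the originally-placebo group. An apparent delay would remain. A reader might also take the randomization-date fallback as a second source of bias; as written, it is not one.

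**Conclusion.** The point holds as a minor one. Read literally, the single origin overstates any Period 3 time to TE-ADA/NAb in the PBO/IXE80Q4W group by 12.0 weeks at nominal visits (11.4 to 12.6 with the Week 12 window), for up to 73 of 146 patients: those randomized to placebo who go on to start ixekizumab.

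This rests on two assumptions. Study treatment in the formula carries the meaning it has in the population definitions, and a Period 3 summary is in fact produced. How far quartiles or medians would be affected cannot be stated, because the documents give no ADA incidence and these may not be estimable.

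Period 2 analyses, including the log-rank test, are correct as planned. The primary and major secondary tests, the sample size and the type I error control are untouched.

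**What to change.** Add a sentence to SAP 6.16.2.1. For analyses beyond Period 2, time to TE-ADA/NAb is counted from the date of first ixekizumab injection: Week 0 for patients randomized to ixekizumab and Week 12 for those randomized to placebo, matching Table RHBQ.6.8. Keep Week 0 as the origin in both arms for Period 2.

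Move the fallback censoring date to the same first-ixekizumab date in those later analyses. The only purpose is to keep it consistent with the new origin and avoid negative times.

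Add a footnote to any Period 3 output. It should say that the originally-placebo group has its first scheduled post-ixekizumab sample about 12 weeks after first exposure, so its times are not directly comparable with those of IXE80Q2W/IXE80Q4W.

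The cost is a short wording change, one derived date in the ADA dataset and one footnote. No new data are needed. The remaining downside is the sparse sampling, which the new origin does not cure.
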